#### **5.5.1.2 Secondary endpoints**

After the 14th dose (Day 14), for BI 1467335:

- $AUC_{\tau,14}$  (area under the concentration-time curve of the analyte in plasma over the dosing interval after administration of the 14th dose)
- $C_{max,14}$  (maximum measured concentration of the analyte in plasma following administration of the 14th dose)

#### **5.5.1.3 Further parameters of interest**

Further pharmacokinetic parameters will be calculated as feasible and may include (but are not limited to):

For DI 629956 and CD 6652 (major metabolites of BI 1467335):

- Same parameters as mentioned in 5.5.1.1 and 5.5.1.2 for BI 1467335
- $RAUC_{x,M/P}$  (ratio of the AUC value of the metabolite versus AUC value of the parent compound). To be calculated for AUCs on Day 1, 14 and 28, if feasible.
- $RC_{max, M/P}$  (ratio of the  $C_{max}$  value of the metabolite versus  $C_{max}$  value of the parent compound).

Proprietary confidential information © 2018 Boehringer Ingelheim International GmbH or one or more of its affiliated companies

For BI 1467335, DI 629956 and CD 6652

After the first dose (Day 1) if the data allows:

- $AUC_{0-tz}$  (area under the concentration-time curve of the analyte in plasma over the time interval from 0 to the last quantifiable data point)
- $AUC_{0-\infty}$  (area under the concentration-time curve of the analyte in plasma over the time interval from 0 extrapolated to infinity)
- $\%AUC_{tz-\infty}$  (the percentage of  $AUC_{0-\infty}$  obtained by extrapolation)
- $AUC_{t1-t2}$  (area under the concentration-time curve of the analyte in plasma over the time interval  $t_1$  to  $t_2$ )
- $t_{max}$  (time from dosing to maximum measured concentration of the analyte in plasma)
- $\lambda_z$  (terminal elimination rate constant in plasma)
- $t_{1/2}$  (terminal elimination half-life of the analyte in plasma)
- $MRT_{ex}$  (mean residence time of the analyte in the body after oral administration)
- (apparent clearance of the analyte in the plasma after extravascular administration), *for BI 1467335 only*
- $V_z/F$  (apparent volume of distribution during the terminal phase after extravascular administration), *for BI 1467335 only*
- $Ae_{t1-t2}$  (amount of analyte that is eliminated in urine from the time interval  $t_1$  to  $t_2$ )
- $fe_{t1-t2}$  (fraction of administered drug excreted unchanged in urine from time point  $t_1$  to  $t_2$ )
- $CL_{R, t1-t2}$  (renal clearance of the analyte in plasma from the time point  $t_1$  to  $t_2$ )

After the 14th dose (Day 14) and the 28th dose (Day 28):

- $AUC_{t1-t2,N}$  (area under the concentration-time curve of the analyte in plasma over the time interval  $t_1$  to  $t_2$  following N doses)
- (time from the Nth dosing to maximum concentration of the analyte in plasma following N doses)
- $\lambda_{z,N}$  (terminal rate constant in plasma following N doses)
- $t_{1/2,N}$  (terminal half-life of the analyte in plasma following N doses)
- $MRT_{ex,N}$  (mean residence time of the analyte in the body following N orally administered doses)
- $CL_{N}/F$  (apparent clearance of the analyte in the plasma following N doses of extravascular administration; calculated as Dose/ $AUC_{0-24,N}$ ), *for BI 1467335 only*
- $V_{z,N}/F$  (apparent volume of distribution during the terminal phase  $\lambda_z$  following N doses of extravascular administration; calculated as  $CL_{N}/F/\lambda_{z,N}$ ), *for BI 1467335 only*
- $R_{A,Cmax,N}$  (accumulation ratio based on  $C_{max}$  after N doses)
- $R_{A,AUC,N}$  (accumulation ratio based on  $AUC_{\tau}$  after N doses)
- $Ae_{t1-t2,N}$  (amount of analyte that is eliminated in urine following N doses from the time point  $t_1$  to time point  $t_2$ )
- $fe_{t1-t2,N}$  (fraction of analyte eliminated in urine following N doses from time point  $t_1$  to time point  $t_2$ )
- $CL_{R,t1-t2,N}$  (renal clearance of the analyte in plasma from the time point  $t_1$  to time point  $t_2$  following N doses)

On days 2, 4, 7, 10, 14, 15, 17, 21, 25, 26 and 28:

- $C_{pre,N}$  (predose concentration of the analyte in plasma immediately within 30 minutes before administration of the  $N^{th}$  dose)

Further pharmacokinetic parameters might be calculated as appropriate.

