#### *Pharmacokinetics in healthy subjects*

Following both single and multiple doses of 10 and 15 mg, BI 1467335 Cmax and AUC0-24 increased in a more than dose proportional manner on Days 1, 14 and 28 ([Figure 1.2: 1](#)). Resulting from the accumulation of BI 1467335 following repeat oral dosing, quantifiable BI

Proprietary confidential information © 2018 Boehringer Ingelheim International GmbH or one or more of its affiliated companies

1467335 concentrations could be measured up to 4 h and 8 h postdose for 10 and 15 mg respectively on Day 1; and up to 24 h postdose on Days 14, and Day 28. Resulting from the limited time period over which quantifiable BI 1467335 concentrations could be measured on Day 1; the resulting  $AUC_{0-24}$  values on Day 1 need to be regarded with caution, as they may be underestimates, due to the large number of concentrations below the assays lower limit of quantification

The observed apparent elimination half-life (gMean) for BI 1467335 is significantly shorter on Day 1 (<1 h) compared to Days 14 and 28, (<4 h following 10 mg and < 9 h following 15 mg on Day 28). Despite the short apparent elimination half-lives, BI 1467335 significantly accumulates following q.d. dosing. For 10 mg q.d.,  $C_{max}$  increased by approximately 26-fold on Day 14 and 40-fold on Day 28, and  $AUC_{0-24}$  increased by approximately 58-fold on Day 14 and 159-fold on Day 28. For 15 mg q.d. dosing,  $C_{max}$  increased by approximately 14-fold on Day 14 and 16-fold on Day 28, and  $AUC_{0-24}$  increased by approximately 72-fold on Day 14 and 82-fold on Day 28.

Taking all the BI 1467335 data together, including trough concentrations, 1 h postdose samples along with  $AUC_{0-24}$  values, they suggest that steady state may be attained close to Day 14 following 15 mg q.d., whereas it was not attained by Day 14 following 10 mg q.d.. Following 10 mg q.d.,  $C_{max}$  and  $AUC_{0-24}$  are approximately 54% and 180% higher respectively on Day 28 compared to that on Day 14, whereas following 15 mg q.d.,  $C_{max}$  and  $AUC_{0-24}$  are approximately 13 and 15 % higher respectively on Day 28 compared to that on Day 14. For further details, please refer to the current 'Investigator's Brochure (IB)' [\[c04751792\]](#).

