Thus, BI 1467335 appears to display both dose and time dependent kinetics, where BI 1467335  $C_{max}$  and  $AUC_{0-24}$  values on Days 14 and 28 are greater than predicted from Day 1 data. BI 1467335 accumulation may in part be due to irreversible binding to AOC3 enzymes which are present in many different tissues within the body (Target Mediated Drug Disposition). This may explain the observation that steady state appears to be attained earlier following 15 versus 10 mg q.d. the highest dose tested to date.

[figure not shown]

Figure 1.2: 1

Geometric Mean BI 1467335 concentration-time profiles following single and multiple BI 1467335 dosing, 10 mg q.d. (left graph) and 15 mg q.d. (right graph), to healthy subjects on Days 1, 14 and 28 (up to 24 h postdose, semi-log scale)

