## **2. RATIONALE, OBJECTIVES, AND BENEFIT - RISK ASSESSMENT**

### **2.1 RATIONALE FOR PERFORMING THE TRIAL**

An association between NAFLD/NASH and impaired renal function was consistently shown in numerous epidemiological studies [[P16-05590](#)] and may be due to common underlying inflammatory pathways in liver and kidney. BI 1467335 is going to enter phase IIb in a NASH population. Taking the published epidemiological data into consideration this may be associated in up to 20% of NASH patients with a reduced GFR < 60 ml/min i.e. at least moderate renal impairment.

Based on both the preclinical and ongoing clinical phase I study 1386.8, renal clearance is considered to be involved in the elimination of BI 1467335, especially following multiple dosing. The study is conducted to support the safe inclusion of NASH patients who may have moderate renal impairment in Phase IIb/III studies.

The PK will be investigated during a 4 week treatment with 10 mg of BI 1467335 q.d. which has already been shown to be well tolerated in healthy subjects. A dose of 10 mg is the planned maximum therapeutic dose in a NASH population. Currently 20 mg q.d. is being investigated in HVs. Preliminary 15 mg q.d. in HVs on Day 28 resulted in gMean  $C_{max}$  and  $AUC_{0-24}$  values approximately 2.6 and 4.7-fold higher than those observed on Day 28 following 10 mg q.d..

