### **3.2 DISCUSSION OF TRIAL DESIGN, INCLUDING THE CHOICE OF CONTROL GROUP**

The study will be conducted according to a multiple-dose, open-label design with matched-groups.

BI 1467335 displays non-linear, time dependent kinetics with a 40-fold higher  $C_{max}$  and 159-fold higher  $AUC_{0-24}$  on Day 28 compared to Day 1 (see [Section 1.2](#), refers to 10 mg of BI 1467335 q.d., the dose selected for the planned study). Since steady state PK is not predicted by single dose data, multiple doses are required to assess the clinically relevant data as BI 1467335 is being developed for chronic dosing. Based on preliminary evaluation, treatment duration of 4 weeks, the currently maximum treatment duration in healthy subjects, and a dose regimen of 10 mg q.d. should provide close to steady state conditions. This should also reliably exclude any transient effects.

The resulting group sizes (see [Section 7.1](#)) are considered to be sufficient for the exploratory evaluation of pharmacokinetics. The assignment of matched healthy volunteers is a useful method to control for other factors which may influence the pharmacokinetics of BI 1467335 in a renal impaired population.

The open-label treatment is not expected to bias results, since the primary endpoints are derived from measurement of plasma concentrations of the analytes provided by a bioanalytical laboratory. It is also considered sufficiently accurate as the trial observations are objective (PK, laboratory) and over-reporting of AEs is unlikely.

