### **7.3.5      Pharmacokinetic analyses**

The pharmacokinetic parameters listed in [Section 5.5.1](#) for drug BI 1467335 will be calculated according to the BI SOP 'Standards and processes for analyses performed within Clinical Pharmacokinetics/Pharmacodynamics' [[001-MCS-36-472](#)].

Subjects who are not included in the PKS (refer to [Section 7.3.1](#)) will be reported with their individual plasma / urine concentrations and individual pharmacokinetic parameters; however, they will not be included in descriptive statistics for, pharmacokinetic parameters or other statistical assessment.

Only concentration values within the validated concentration range and actual sampling times will be used for the calculation of pharmacokinetic parameters. Concentrations used in the pharmacokinetic calculations will be in the same format provided in the bioanalytical report, (that is, to the same number of decimal places provided in the bioanalytical report).

Descriptive evaluations of PK parameters listed in 5.5.1 are based on PKS.

The following descriptive statistics will be calculated for analyte concentrations as well as for all pharmacokinetic parameters: N, geometric mean, geometric coefficient of variation, arithmetic mean, arithmetic coefficient of variation, standard deviation, minimum, median, and maximum. The data format for descriptive statistics of concentrations will be identical with the data format of the respective concentrations. The descriptive statistics of pharmacokinetic parameters will be calculated using the individual values with the number of decimal places as provided by the evaluation program. Then the individual values as well as the descriptive statistics will be reported with three significant digits in the clinical trial report.

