### 6.3 SUBJECT SETS ANALYSED

- Treated set (TS):

This subject set includes all subjects who were dispensed study medication and were documented to have taken at least one dose of investigational treatment.

This is the full analysis set population in the sense of ICH-E9 ([1](#)). It is used for safety analyses.

Plasma and urine concentration data and parameters of a subject will be included in the statistical pharmacokinetic (PK) analyses if they are not flagged for exclusion due to a protocol deviation relevant to the evaluation of PK (to be decided no later than in the Report Planning Meeting) or due to PK non-evaluability (as revealed during data analysis, based on the criteria specified below). Exclusion of a subject's data will be documented in the CTR.

Relevant protocol deviations may be:

- Incorrect dose of trial medication taken
- Use of restricted medications.

Plasma and urine concentrations and/ or parameters of a subject will be considered as non-evaluatable, if for example:

- the subject experienced emesis that occurred at or before two times median  $t_{max}$  of the respective treatment (Median  $t_{max}$  is to be determined excluding the subjects experiencing emesis),
- missing samples/ concentration data at important phases of PK disposition curve.

  

- PK analysis set (PKS):  
The PK analysis set (PKS) includes all subjects in the TS who provide at least one PK parameter that was defined as primary or secondary endpoint and was not excluded according to the description above. Thus, a subject will be included in the PKS, even if he/she contributes only one PK parameter value to the statistical assessment.
- PK statistical analysis set (PKS-stat):  
This subject set includes all subjects from the PKS who built a subject pair of renal impaired subject and his matching healthy volunteer control and provide at least one PK parameter that was defined as primary or secondary endpoint and was not excluded according to the description above.

The descriptive analysis of PK concentrations will be based on the ADS ADPC as described at the beginning of [Section 7](#).

Table 6.3: 1 Analysis sets for endpoints/data description

Endpoint/data description	Analysis set		
	TS	PKS	PKS-stat
Safety assessments		X	
Primary and secondary analyses of primary, secondary and further PK endpoints			X
Further analyses of primary and secondary PK endpoints		X	
Descriptive evaluations of primary, secondary and further PK endpoints		X	

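### Is Day 14 Dose/AUC wrongly reported as apparent clearance, given that steady state was not reached by Day 14 at 10 mg q.d.?

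*Protocol*

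**What the plan says.** Protocol section 5.5.1.3 (Further parameters of interest) gives one list for Day 14 and Day 28. For the parent drug it includes CL_N/F, the "apparent clearance of the analyte in the plasma following N doses of extravascular administration; calculated as Dose" over AUC0-24,N, and Vz,N/F, the "apparent volume of distribution during the terminal phase", obtained by dividing CL_N/F by the terminal rate constant. Neither carries a steady-state condition. The section opens by saying that such parameters are calculated where feasible and that the list is one of possibilities.

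Section 1.2 reports, for healthy subjects in an earlier study, that steady state may be attained close to Day 14 at 15 mg, "whereas it was not attained by Day 14 following 10 mg q.d". It adds that "BI 1467335 appears to display both dose and time dependent kinetics" and names irreversible binding to AOC3 as a partial explanation. Section 3.2 expects that four weeks at 10 mg q.d. "should provide close to steady state conditions".

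On reporting, section 7.3.5 states: "The following descriptive statistics will be calculated for analyte concentrations as well as for all pharmacokinetic parameters". SAP section 4 says that all protocol analyses will be performed, and the SAP text available does not qualify the formula.

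**The concern.** Over one dosing interval, Dose/AUC equals CL/F when the amount leaving the body in that interval equals the amount absorbed. That is normally argued from steady state. Here the protocol applies the formula on a day when, by its own account, exposure at the trial dose was still rising steeply.

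The question also matters to this trial. Section 2.1 gives as its rationale that "renal clearance is considered to be involved in the elimination of BI 1467335, especially following multiple dosing". A table of Day 14 clearance by renal group is one that a reader could take as a direct answer. If the value reflects the speed of accumulation as much as elimination, a group difference could be misread, and Vz,14/F would inherit the error.

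**Working it through.** **Inputs.** From Protocol section 1.2, at 10 mg q.d. in healthy subjects:
- AUC0-24 accumulation of 58-fold (Day 14) and 159-fold (Day 28) relative to Day 1
- Cmax accumulation of 26-fold and 40-fold
- stated Day 14 to Day 28 rises of about 54% (Cmax) and 180% (AUC0-24)
- apparent half-life below 4 h on Day 28, and below 1 h on Day 1

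The dose is 10 mg q.d. throughout (section 4.1.4).

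**Step 1: reproduce the protocol's figures.** Cmax: 40/26 = 1.54, matching the stated 54%. AUC0-24: 159/58 = 2.74, against the stated 2.80. Rounding of the fold values allows 158.5/58.5 = 2.71 to 159.5/57.5 = 2.77, so the agreement is good for approximate figures.

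**Step 2: what this means for CL_N/F.** At a fixed dose, (CL_14/F)/(CL_28/F) = AUC28/AUC14 = 2.74 to 2.80. At 15 mg the same ratio is 82/72 = 1.14. Vz,14/F relative to Vz,28/F carries the same factor if the half-life is equal on both days. If the Day 14 half-life were 0.5 to 1.25 times the Day 28 half-life (an assumption), the volume ratio would be about 1.4 to 3.5.

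**Step 3: can incomplete accumulation alone explain the gap?** In a linear one-compartment model, AUC28/AUC14 = (1 − e^(−28k))/(1 − e^(−14k)) = 1 + e^(−14k), with k per day. This cannot exceed 2. So within that model at least 2.74/2 = 1.37 to 2.80/2 = 1.40 must come from something else. The dose- and time-dependent kinetics described in section 1.2 are the obvious candidate.

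**Step 4: when is Dose/AUC before steady state still a clearance?** By mass balance over the interval, F·Dose = amount irreversibly lost + gain in recoverable drug. If the gain is small, Dose/AUC equals the average clearance over that interval, whether or not clearance will change later. Take 4 h, the upper limit reported for Day 28, as an assumption for Day 14. The fraction left after 24 h is then 0.5^6 = 1.6%. Linear accumulation at that half-life would be only 1/(1 − 0.0156) = 1.016-fold, so the gain in recoverable drug could shift Dose/AUC by about 1.6% at most. Drug bound irreversibly to AOC3 counts as lost. As the target fills, true clearance falls and Dose/AUC follows it.

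Simulation bears this out. With irreversible binding, a linear half-life of 3.85 h and slow target turnover (all assumed), a Day 28/Day 14 AUC ratio of 2.80 arose while Dose/AUC on Day 14 matched the true interval-average clearance to within 0.01%. When bound drug was allowed to return slowly, Dose/AUC did overstate clearance, by about 1.4-fold in the runs closest to the reported accumulation.

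**Step 5: could a linear model show a biased group ratio?** With equal V/F and a true clearance ratio of 0.50, the Day 14 ratio is 0.5·(1 + √(1 − f)), where f is the healthy group's fraction of plateau on Day 14. For f = 0.50 to 0.95 this reads 0.85 to 0.61. But f = 0.50 needs a half-life of 14 days (336 h), and f = 0.95 needs 3.24 days (78 h), against the reported figure below 4 h. With 4 h in the healthy group and 8 h in the impaired group, the same model gives 0.50, with no bias. This is also the model that step 3 shows cannot produce 2.74.

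**Step 6: what the parameter adds.** Since log(Dose/AUC) = log(Dose) − log(AUC) and the dose is the same for everyone, the impaired/healthy geometric mean ratio of CL_14/F is exactly 1 divided by that of AUC0-24,14 in the same subjects. AUCτ,14 is already a secondary endpoint with a paired ANOVA and a 90% confidence interval (SAP sections 7.4 and 7.5.2).

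**The case for a change.** The strongest opposing case is that calculating parameters where feasible screens for computability, not validity. Dose/AUC0-24 can be computed whenever the AUC exists, so nothing in the wording keeps a non-steady-state value out of the tables. The reported half-life is only apparent, and quantifiable 24 h concentrations on Days 14 and 28 leave room for a slow return phase that would make Day 14 Dose/AUC too high. A footnote would cost almost nothing.

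Much of this stands. The Day 14 values should not be read as steady-state clearance or volume, and a return phase cannot be excluded. The reference data are also preliminary, from 9 actively treated healthy subjects at 10 mg who took an oral solution rather than this tablet. They settle the matter in neither direction.

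It does not follow that the values are not a clearance, or that the tables would mislead. The protocol indexes the parameter by dose number, not as steady state, and prints the formula. It plans predose concentrations on 11 days and both accumulation ratios beside it, and section 1.2 discloses that steady state was not reached. A pharmacokineticist has what is needed to read the number correctly.

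One could also ask for renal clearance, which needs no steady state, to be put through the paired model. That is a separate preference. Renal clearance on Days 14 and 28 is already listed and summarised, and SAP Table 6.3:1 assigns "Primary and secondary analyses of primary, secondary and further PK endpoints" to the paired set, so it may already be covered.

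**Conclusion.** The two passages do sit awkwardly together, and the 2.74 to 2.80 factor is correct. It is a ratio between days in one healthy dose group, though. It is not a bias estimate and says nothing about the renal group ratio. How far Day 14 Dose/AUC departs from the clearance in that interval depends on how much drug returns from tissue or target. The departure is about 1.6% at most if the half-life below 4 h governs and binding is irreversible, and about 1.4-fold in the slow-return simulations. The documents do not choose between these.

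What remains is the label on an optional descriptive parameter. Its group comparison repeats the planned Day 14 AUC comparison in inverted form, so dropping or relabelling it would change no primary or secondary estimate, confidence interval or conclusion. A table footnote saying that steady state is not assumed is ordinary reporting practice and needs no change to the protocol or SAP. SAP text that is not visible may already deal with it.

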## **5.5.2 Methods of sample collection**

### **5.5.2.1 Plasma sampling for pharmacokinetic analysis**

For quantification of BI 1467335 plasma concentrations, approx. 2.7 mL of blood will be taken from an antecubital or forearm vein into a K3-EDTA (tripotassium ethylenediaminetetraacetic acid)-anticoagulant blood drawing tube at the times indicated in the [Flow Chart](#). Blood will be withdrawn by means of either an indwelling venous catheter or by venipuncture with a metal needle.

All blood samples will be centrifuged using a cooled centrifuge at about 2000 x g to 4000 x g and at a temperature of 4 - 8°C for at least 10 minutes (intermittent storage on ice). The obtained K3-EDTA plasma will be split into two cryotubes (e.g. Nunc tubes) which will be frozen immediately and not later than 60 min after blood sampling with interim storage on ice. One of the aliquots should contain at least 0.5 mL plasma which was pretreated with 10 µL phenelzine solution (approx. 25 mM/L). The second aliquot containing the remaining plasma will be used as analytical back-up sample. Until transfer on dry ice to the analytical laboratory, the plasma samples will be stored frozen and in upright position at about -20°C or below at the clinical site and at the analytical laboratory until analysis.

After completion of the trial the plasma samples may be used for further methodological investigations, e.g. for stability testing, assessment of metabolites. However, only data related to the analyte and/or its metabolite(s) will be generated by these additional investigations. The study samples will be discarded after completion of the additional investigations but not later than 5 years upon the final study report has been signed.

At a minimum, the sample tube labels should list the following information: BI trial number, subject number, visit, and planned sampling time. Further information such as matrix and analyte may also be provided.

The study samples will be discarded after completion of the additional investigations but not later than 5 years upon the final study report has been signed.

